### 6.5.1.1 Capecitabine

Criteria for interruption of capecitabine alone (Table 6):

**Table 6 Criteria for Interruption of Capecitabine Alone**

| Special Criteria for Interrupting Capecitabine Only
[Grading as per CTCAE (v4.0)]  |
|---|
| 
 
• Palmar-plantar erythrodysesthesia (PPE) (Hand-foot syndrome) <math>\geq</math> CTCAE grade 2.
 
• Additional grade 3 toxicity which is felt to be attributable to capecitabine alone
 
 |

*Criteria for reinitiating capecitabine:* The AE of concern in Table 6 must have resolved to grade 1 or less prior to reinitiating capecitabine. As per missed doses, capecitabine should not be reinitiated on the 1 week of scheduled rest.

### 6.5.2 Dose Reduction

As initial measure for the management of side effects, treatment with nintedanib and capecitabine should be temporarily interrupted until the specific adverse reaction has resolved to levels that allow continuation of therapy. Nintedanib and capecitabine treatment may be resumed at a reduced dose. Dose adjustments of nintedanib based on individual safety and tolerability are recommended as described in **Table 7 and Table 8**.

The following dose levels will be used in case dose adjustments are required for management of undue toxicity.

**Table 7 Nintedanib Dose Level Reduction Scheme**

| Dose Level | Nintedanib                         |
|-------------------|---|
| 1                 | 200 mg (2 x 100 mg) po bid(starting dose) |
| - 1               | 150 mg po bid                             |
| - 2               | 100 mg po, qAM and 150 mg po, qPM         |
| - 3   | 100 mg po bid                 |

1 This table is based upon a phase 1 dose and/or recommended Phase 2 dose of 200 mg bid. The dose level would not proceed beyond dose level -2 in that circumstance. Should the recommended phase 2 dose be less than 200 mg bid, dose levels would be adjusted accordingly.

2 Patients requiring greater than two dose reductions will be taken off protocol therapy. Dose level -3 would only be utilized in the case that nintedanib was initiated at a dose of less than 200 mg bid.

**Table 8 Capecitabine Dose Level Reduction Scheme**

| Dose Level       | Capecitabine   |
|------------------|--|
| 1                | 2000 mg/m  /day (starting dose), divided bid |
| - 1              | 1500 mg/m  /day, divided bid                 |
| - 2              | 1250 mg/m  /day, divided bid                 |
| - 3  | 1000 mg/m  /day, divided bid     |

- 1 This table is based upon a phase 1 dose and/or recommended Phase 2 dose of 2000 mg/m^2/day. The dose level would not proceed beyond dose level -2 in that circumstance. Should the recommended phase 2 dose be less than 2000 mg/m^2/day, dose levels would be adjusted accordingly.
- 2 Patients requiring greater than two dose reductions will be taken off protocol therapy. Dose level -3 would only be utilized in the case that capecitabine was initiated at a dose of less than 2000 mg/m^2/day.

**Note:** If the dose of nintedanib (BIBF1120) or capecitabine has to be reduced due to toxicity, it will stay on the lower dose level for the entire time of administration.

### 6.5.3 Management of specific AEs

- Diarrhea
- Nausea and vomiting
- Liver Enzyme Elevations

**Table 9 Recommended Dose Adjustments for Nintedanib (BIBF1120) and Capecitabine**

| CTCAE (v4.0) Adverse Reactions   | Dose Adjustment  |
|--|--|
| Diarrhea ≥ grade 2 for more than 7 consecutive days despite optimal antidiarrheal treatment
OR
Diarrhea ≥ grade 3 despite optimal antidiarrheal treatment | 1st episode 
 
• Reduce 1 dose level
 
         |
| Vomiting ≥ grade 2
AND/OR
Nausea ≥ grade 3 despite optimal anti-emetic treatment  | 2nd episode 
 
• Reduce 1 further dose level
 
 |

|   |  |
|---|--|
| 
AST and/or ALT elevations > 3 X ULN in conjunction with bilirubin of > 1.5 X ULN
 
OR
 
AST and/or ALT elevations of > 5 X ULN
 | 
3rd episode
 
 
• Stop treatment
 
 |
|---|--|

Management of all other AEs:

**Table 10 Management of Additional Adverse Events for Either Drug**

| Grade of Event   | During a Course of Therapy   | Dose Adjustment for Next Cycle   |
|--|--|--|
| ≤ Grade 1  | No change in dose.   | Resume at same dose level  |
| Grade 2
1 st occurrence | Hold until ≤ Grade 1   | Resume at same dose level.   |
| Grade 2
2 nd occurrence | Hold until ≤ Grade 1   | Resume at 1 dose level lower   |
| Grade 2
3 rd occurrence | Hold until ≤ Grade 1   | Resume at 1 dose level lower   |
| Grade 2
4 th occurrence | Hold until ≤ Grade 1   | Permanently discontinue  |
| Grade 3   | Hold until < Grade 2   | Resume at 1 dose level lower, if indicated   |
| Grade 4   | Discontinue permanently or, if physician deems it to be in the patient's best interest to continue, interrupt until resolved to grade 0-1. | Permanently discontinue OR
Reduce capecitabine by 50% AND
Reduce nintedanib 1 dose level |

1 Excludes sub-optimally treated grade 2 diarrhea/ nausea and hypertension. At the investigator's discretion, dose reduction of capecitabine may be pursued after the first occurrence of grade 2 Palmoplantar erythrodysesthesia.

2 Participants requiring a delay of > 2 weeks should go off protocol therapy.

3 Participants requiring > 2 dose reductions should go off protocol therapy.

Recommended management for nausea and vomiting: antiemetics.

Recommended management for diarrhea: Loperamide antidiarrheal therapy. Dosage schedule: 4 mg at first onset, followed by 2 mg with each loose motion until diarrhea-free for 12 hours (maximum dosage: 16 mg / 24 hours) Adjunct antidiarrheal therapy is permitted and should be recorded when used.

Of note, in many cases, it will be difficult to firmly establish one of the agents as being causative of the adverse event (i.e. fatigue, nausea or diarrhea). As suggested above, in these instances, temporary cessation and/or dose reductions of both nintedanib and capecitabine are to be carried out. In the circumstance that an adverse event, which is not otherwise described herein, is felt to be clearly attributed to one of the two agents, but not the other, the putative inciting agent should be held, with dose modification of that agent only, as appropriate.

Patients should PERMANENTLY discontinue treatment in the event of:

- Intolerable Adverse Events (CTCAE grade 3 or 4) that cannot be managed by dose reduction.
- Withdrawal of informed consent.
- AEs requiring a delay in therapy of > 2 weeks (except as above, in the case that a patient is felt to be deriving clinical benefit and, this is first discussed and agreed upon between the individual investigator and the principal investigator.).

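### After a grade 4 event, Table 10's option to continue halves capecitabine to 1000 mg/m²/day, a level that Table 8 does not allow for patients who started at 2000 mg/m²/day

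*Combined protocol and SAP*

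**What the plan says.** The grade 4 row of Table 10 gives two courses. One is permanent discontinuation. The other applies "if physician deems it to be in the patient's best interest to continue, interrupt until resolved to grade 0-1"; the adjustment for the next cycle is then "Reduce capecitabine by 50% AND" a one-level reduction of nintedanib.

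Table 8 (Section 6.5.2) sets the capecitabine ladder:

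- level 1: "2000 mg/m 2 /day (starting dose), divided bid"
- level -1: "1500 mg/m 2 /day, divided bid"
- level -2: "1250 mg/m 2 /day, divided bid"
- level -3: "1000 mg/m 2 /day, divided bid"

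Footnote 1 addresses a 2000 mg/m²/day start: "The dose level would not proceed beyond dose level -2 in that circumstance". Footnote 2 takes patients who need more than two reductions off protocol therapy and adds: "Dose level -3 would only be utilized in the case that capecitabine was initiated at a dose of less than 2000" mg/m²/day. Section 6.5.2 introduces Tables 7 and 8 as the levels to apply when toxicity requires a dose change. A note under Table 8 keeps a reduced dose in force for the rest of treatment.

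Sections 4.1.2 and 6.2 record dose level 2 as the RP2D, and Table 2 gives it a capecitabine dose of 2000 mg/m² daily. Phase I dose level 1 has the same capecitabine dose.

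**The concern.** The two tables govern the same decision, the capecitabine dose after toxicity, and on one branch they give incompatible answers. A physician who continues treatment after a grade 4 event is sent by Table 10 to a dose that Table 8 withholds from every patient who started at 2000 mg/m²/day. No text makes the grade 4 row an exception.

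What is at stake is safety and consistency. Two sites enrol, and they could handle the same event differently: one might follow the 50% instruction, the other might treat the resulting dose as unavailable. Because a reduced dose is kept, the difference would last for the remainder of treatment. It would also blur which courses of treatment count as protocol deviations, and the reporting of dose intensity.

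**Working it through.** **Inputs**

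- Starting dose: 2000 mg/m²/day (Table 2, dose levels 1 and 2; Table 8, level 1).
- Ladder: 2000, 1500, 1250, 1000 mg/m²/day (Table 8).
- Lowest level open to a 2000 start: level -2, 1250 mg/m²/day (Table 8, footnote 1).
- Grade 4 cut if treatment continues: 50% (Table 10).

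**Step 1: no earlier reduction.** The starting and current dose are the same, so the base for the 50% does not matter.

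0.50 × 2000 = 1000 mg/m²/day.

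This equals level -3 exactly. Against the limit: 1250 − 1000 = 250 mg/m²/day below it. Put as reductions from the start, level -2 is 1 − 1250/2000 = 37.5%, while Table 10 calls for 50%.

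**Step 2: earlier reduction.** Table 10 does not state the base, so both readings are shown.

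| Dose at the event (mg/m²/day) | 50% of starting dose | 50% of current dose |
|---|---|---|
| 1500 (level -1) | 1000, level -3 | 0.50 × 1500 = 750, not listed |
| 1250 (level -2) | 1000, level -3 | 0.50 × 1250 = 625, not listed |

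The 750 and 625 figures therefore hold only if the current dose is the base. Under either base, the result for a 2000 start is not a dose that Table 8 permits.

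**Step 3: the two-reduction limit.** From 2000 to 1000 is one act of reduction but three steps on the ladder (2000 to 1500, to 1250, to 1000). Counted as acts, it is within the limit of two; counted as steps, it exceeds it. A patient who reached 1250 one level at a time has already had two reductions, so a further cut would be a third on either count. The corresponding footnote in Table 10 (footnote 3) is marked on the grade 3 row and not on the grade 4 row, so it does not settle the matter there.

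**Step 4: the other branch.** Permanent discontinuation involves no dose, so it conflicts with nothing in Table 8.

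**The case against.** The best case for the plan is that the grade 4 row is a deliberate special rule. Within one cell it uses a percentage for capecitabine and a level for nintedanib, and the grade 2 and grade 3 rows speak only of levels. Footnote 2 of Table 8 joins the level -3 restriction to the limit on the number of reductions, so the footnotes might be meant for stepwise reductions only. Section 6.5.2 also describes its adjustments as recommended. This makes the conflict less certain but does not remove it. The same section goes on to say that the listed levels are the ones to be used, footnote 2 restricts level -3 without exception, and the halved dose coincides with that restricted level.

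On counting, the footnotes refer to reductions and not to levels, so the plain reading is that one 50% cut is one reduction. That is reasonable, but the placing of footnote 3 leaves room for doubt.

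Three stronger readings are tempting and are not supported:

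- *A reader might infer that a site cannot comply with both tables after a grade 4 event.* It can, by discontinuing. The conflict arises only when the physician chooses to continue.
- *A reader might infer that any patient already reduced would fall below every listed level.* That assumes the 50% is taken from the current dose, which Table 10 does not say.
- *A reader might infer that the primary endpoint is compromised.* Section 12.3 counts progression or death before 18 weeks as failure. Stopping for toxicity is not a listed failure, and time on treatment is not part of the definition.

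The scope is also limited: Table 10 covers events other than the diarrhoea, nausea and vomiting, and liver enzyme events assigned to Table 9.

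**Conclusion.** The concern stands as an internal inconsistency, confined to the discretionary continuation branch of Table 10's grade 4 row. For a patient who started at 2000 mg/m²/day with no earlier reduction, that branch gives 1000 mg/m²/day, which is 250 mg/m²/day below the limit in Table 8 and is a level reserved for lower starts. This result needs no assumption about the base for the 50%. The further results of 750 and 625 mg/m²/day depend on the current-dose reading.

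The consequence is for safety and for uniform dosing across sites. The documents give no basis for estimating how many patients would be affected, and any effect on 18-week PFS would be indirect and is not quantified. No view is taken here on which dose or rule is correct.

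**What to change.** Amend Section 6.5 in three respects:

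1. Reconcile the grade 4 row of Table 10 with Table 8 and its footnotes, so that a single rule applies to patients who start capecitabine at 2000 mg/m²/day.
2. If a percentage cut remains, state whether it is taken from the starting or the current dose.
3. State how a grade 4 cut counts toward the limit of two reductions, and whether footnote 3 of Table 10 applies to the grade 4 row.

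The clinical team decides which rule stands. The cost is protocol wording in an amendment. The sample size, the endpoint definition and the analysis are unchanged.

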## 6.6 General Concomitant Medication and Supportive Care

### 6.6.1 Additional precautions and supportive care.

- *Diarrhea*

Diarrhea was the most frequently reported gastro-intestinal event and appeared in close temporal relationship with the administration of docetaxel in the clinical trial LUME-Lung 1. The majority of patients had mild to moderate diarrhoea. 6.3 % of the patients had diarrhoea of grade  $\geq 3$  in combination treatment compared to 3.6 % treated with docetaxel alone. Diarrhea should be treated at first signs with adequate hydration and antidiarrheal medicinal products, e.g. loperamide, and may require interruption, dose reduction or discontinuation of therapy with nintedanib.

- *Nausea and vomiting*

Nausea and vomiting, mostly of mild to moderate severity, were frequently reported gastrointestinal adverse events in the clinical trial LUME-Lung 1. Interruption, dose reduction or discontinuation of therapy with nintedanib (BIBF1120) may be required despite appropriate supportive care. Supportive care for nausea and vomiting may include medicinal products with anti-emetic properties, e.g. glucocorticoids, anti-histamines or 5-HT3 receptor antagonists and adequate hydration.

In the event of dehydration, administration of electrolytes and fluids is required. Plasma levels of electrolytes should be monitored, if relevant gastrointestinal adverse events occur.

- *Neutropenia and Sepsis*

A higher frequency of neutropenia of CTCAE grade > 3 was observed in patients treated with nintedanib (BIBF1120) in combination with docetaxel as compared to treatment with docetaxel alone in the clinical trial LUME-Lung 1. Subsequent complications such as sepsis or febrile neutropenia have been observed.

- *Hepatic Function*

The safety and efficacy of nintedanib has not been studied in patients with moderate (Child Pugh B) or severe (Child Pugh C) hepatic impairment. Therefore treatment with nintedanib (BIBF1120) is not recommended in such patients. Administration of nintedanib was associated with an elevation of liver enzymes (ALT, AST, ALKP (alkaline phosphatase), and bilirubin, with a potentially higher risk for female patients.

These increases were reversible in the majority of cases and not associated with clinically manifest liver disorders. Hepatic transaminases, ALKP and bilirubin levels are recommended to be closely monitored after start of therapy with nintedanib (BIBF1120) (periodically, i.e. in the combination phase with docetaxel at the beginning of each treatment cycle). If relevant liver enzyme elevations are measured, interruption, dose reduction or discontinuation of the therapy with nintedanib may be required (see **Appendix C** for procedures for follow-up for potential drug-induced liver injury).

### **6.6.2 Concomitant medications**

Additional chemo-, immuno-, hormone- or radiotherapies are not allowed during the active treatment period of this trial. Palliative radiotherapy may be permitted for symptomatic control of pain from bone metastases after discussion with the Principle Investigator, provided that the radiotherapy does not affect target lesions, and the reason for the radiotherapy does not reflect progressive disease.

Metabolism of nintedanib by CYP450 enzymes plays only a minor role (5%). Additionally, nintedanib did not show relevant induction or inhibition of the major drug metabolizing cytochrome P450 enzymes and specifically no irreversible CYP3A4 inhibition. However, if co-administered with nintedanib, strong P-gp inhibitors may increase exposure to nintedanib (e.g. ketoconazole or erythromycin). Thus, such medications are to be avoided unless deemed to be absolutely necessary. In such cases, patients should be monitored closely for tolerability of nintedanib. Management of side effects may require interruption, dose reduction or discontinuation of therapy with nintedanib.

Strong P-gp inducers, e.g. rifampicin, carbamazepine, phenytoin, and St. John's Wort, may decrease exposure to nintedanib. Co-administration with Nintedanib and potential alternative therapies should be carefully considered.

Because there is a potential for interaction of drug with other concomitantly administered drugs, the electronic case report form (eCRF) must capture the concurrent use of all other drugs, over-the-counter medications, or alternative therapies. The Investigator should be alerted by the study clinical research coordinator if the participant is taking any agent known to affect or with the potential to affect selected CYP450 isoenzymes, P-gp inducers or inhibitors.

Aluminum hydroxide and magnesium hydroxide containing products should be avoided while taking capecitabine. Investigation has documented increase plasma levels of capecitabine and one metabolite with the use of Maalox. Post marketing reports indicate that some patients taking both capecitabine and phenytoin experienced toxicity with elevated phenytoin levels. The level of phenytoin should be carefully monitored in patients taking capecitabine and phenytoin doses may need to be reduced.

During cycle 1 of the phase I study, the use of myeloid growth factors (including Neupogen and Neulasta) is not permitted. After cycle 1 and during the phase II study, growth factor support may be utilized at the discretion of the investigator.

Participants may be pretreated for nausea and vomiting with appropriate anti-emetics.

Rescue medication to reverse the actions of nintedanib (BIBF1120) is not available. Potential side effects of nintedanib (BIBF1120) have to be treated symptomatically.

### **6.7 Duration of Treatment**

Participants may remain on study and continue to receive treatment in the absence of disease progression, unacceptable toxicity or withdrawal from study, intercurrent illness that prevents further administration of treatment, participant demonstrates an inability/refusal to comply with oral medication regime, and participant withdraws from study.

### **6.8 Treatment Discontinuation**

Upon treatment discontinuation all end of treatment evaluations and tests will be conducted. All participants who discontinue due to an AE must be followed until the event resolves or stabilizes. Appropriate medical care should be provided until signs and symptoms have abated, stabilized, or until abnormal laboratory findings have returned to acceptable or pre-study limits. The final status of the AE will be reported in the participant's medical records and the appropriate eCRF.

Reasons for treatment discontinuation should be classified as follows:

- Death
- Progressive disease
- Toxicity; related or unrelated toxicity
- Investigator judgment
  - The Investigator may discontinue a participant if, in his/her judgment, it is in the best interest of the participant to do so.
- Noncompliance
- Participant voluntary withdrawal
  - A participant may withdraw from the study at any time, for any reason. If a participant discontinues treatment, an attempt should be made to obtain information regarding the reason for withdrawal.
- Boehringer Ingelheim decision
- NCCN decision

### **6.9 Compliance**

Patients will be supplied with a medication diary to track self-administration of capecitabine and nintedanib (**Appendix D**). After the first cycle, nintedanib pill counts will be performed at the initiation of each subsequent cycle for reconciliation as well as to assess compliance.

## **7 INVESTIGATIONAL PRODUCT**

### **7.1 Active Substance and Source**

Nintedanib is provided as soft gelatin capsules containing a suspension of milled active as the ethane sulphonate salt. It is available for clinical investigations in five dose strengths corresponding to 50 mg (brown, oval capsules), 100 mg (peach or orange, oblong capsules), 125 mg (orange, oblong capsules), 150 mg (brown or orange, oblong capsules) and 200 mg (brown, oblong capsules). The capsule fill is composed of medium chain triglycerides, hard fat and lecithin in addition to the drug substance.

In oncological studies, the 100 mg and 150 mg capsules will be used either with the trial formulation (all capsules orange) or with the intended market formulation (100 mg: peach, 150 mg: brown).

Capecitabine is supplied as biconvex, oblong, film-coated tablets. Capecitabine is available in two strengths: 150 mg (light peach) or 500 mg (peach).

### **7.2 Drug Shipment**

Nintedanib will be provided by Boehringer Ingelheim Pharmaceuticals, Inc. and shipped to the participating site. Boehringer Ingelheim will provide study specific drug order forms.

The date of receipt and the amount of drug received will be documented. Drug shipment records will be retained by the investigational pharmacist or designee.

Commercially available capecitabine will be used during this study. Patients will be given a prescription (or institutional support, case managers, as appropriate) to fill at the pharmacy of their choice prior to the start of each treatment cycle.

### **7.3 Storage and Stability**

#### **7.3.1 Nintedanib**

The current shelf life for all dosage strengths and formulations of nintedanib is 60 months. The expiration date will be supplied in the shipping receipt or on the bottles. The capsules are packaged in child resistant high density polyethylene (HDPE) bottles and have to be stored below 30°C. The capsules should be protected from exposure to high humidity which is ensured by storage in the original package. Please refer to investigator's brochure for complete details.

The Investigator or designate will be responsible for ensuring that the investigational, nintedanib, product is securely maintained in a locked, limited-access facility, as specified by Boehringer Ingelheim and in accordance with the applicable regulatory requirements.

Drug storage temperature will be maintained and recorded, as applicable.

### **7.4 Handling and Disposal**

The Investigator or designee will be responsible for dispensing and accounting for all investigational drug provided by Boehringer Ingelheim exercising accepted medical and

pharmaceutical practices. Study drugs must be handled as cytotoxic agents and appropriate precautions taken per the institution's environmentally safe handling procedures. All investigational drugs will be dispensed in accordance with the Investigator's prescription or written order.

All products dispensed will be recorded on a product accountability record. Records of product lot numbers and dates received will be entered on a product accountability form. It is the Principal Investigator's responsibility to ensure that an accurate record of investigational drug issued and returned is maintained.

Under no circumstances will the Investigator supply investigational drug to a third party or allow the investigational drug to be used in a manner other than as directed by this protocol.

